### 15.4 Laboratory Safety Parameters

Only select clinical laboratory safety parameters will be converted to consistent units according to the International System of Units (SI) before summarization.

As of development of this SAP only Creatinine Clearance and Serum Creatinine will be summarized as below. Any other available data will be included in listings.

The following will be summarized:

- Numeric laboratory parameters: In case the value of a numeric laboratory parameter is below the lower limit of quantification, the lower limit of quantification will be used as the response value for the purpose of calculating the descriptive statistics.
- Laboratory parameters which have an upper and/or lower reference range: Number and percentage of subjects with 6 categories (missing, clinically significant low, not clinically significant low, normal, not clinically significant high, clinically significant high) values at each visit for each parameter will be summarized by treatment group. If a subject has both low and high abnormalities at a given visit, then only the worst value would be displayed in the appropriate category.
- These values will be presented as a shift table, i.e. the distribution of the 6 response categories at each post-baseline visit and the worst post-baseline value across all visits will be classified by the baseline category.

### 15.5 Vital Signs

Vital sign measurements include pulse rate, systolic and diastolic blood pressure (BP) and body weight. The BPs will be assessed in supine and standing positions and the standing minus supine values will be summarized in addition to the separate summaries of the supine and standing position. The mean of the triplicate values at baseline will be calculated, without rounding the result. These calculated means will constitute the analysis values for baseline.

## Statistical Analysis Plan

Potentially clinically significant vital signs will be identified for selected parameters as defined below. These abnormalities will be summarized using at each visit, the last visit and by the worst post baseline values.

- Systolic BP: <90 mmHg, 90-140 mmHg, >140 mmHg – 160 mmHg, >160 mmHg
- Diastolic BP: <50 mmHg, 50-90 mmHg, >90 mmHg – 100 mmHg, >100 mmHg
- Pulse rate: <60 beats per minute (bpm), 60-100bpm, >100 bpm
- Standing minus supine systolic BP  $\leq$ -20 mmHg
- Standing minus supine diastolic BP  $\leq$ -10 mmHg.

### 15.6 ECG

At Baseline (Visit 2) and at every visit thereafter, triplicate 12-lead ECG evaluations will be assessed before, and 1 to 2 hours after the study drug dose administrated at the clinic. The mean of the triplicate ECG values will be calculated, without rounding the result. These calculated means will constitute the analysis values. The original values will be listed only.

The following will be summarized by treatment group and visit:

- Actual values and change from baseline for each ECG parameter will be summarized with descriptive statistics.

The potentially clinically significant ECGs will be identified for selected parameters as defined below. These abnormalities will be summarized using shift tables by visit and the worst value across all visits.

- QTcF:  $\leq$ 450 msec, >450 – 480 msec, >480 – 500 msec, >500 msec.

In addition to the shift table by visit, the highest post-baseline QTcF value during the study for each subject will be tabulated using the categories listed above.

The potentially clinically significant changes from Baseline in ECGs will be identified for selected parameters as defined below. These abnormalities will be summarized by visit and the worst value across all visits.

- QTcF: change  $\leq$ 30 msec, change >30 – 60 msec, change >60 msec.

In addition to the summary by visit, the highest post-baseline QTcF change during the study for each subject will be tabulated using the categories listed above.

### 15.7 Physical and Neurological Examination

Physical exam data will be only listed with no summary tables.

## 15.8 Other Safety Variables

### 15.8.1 Columbia Suicide Severity Rating Scale (C-SSRS)

The Columbia-Suicide Severity Rating Scale Screening/Baseline Version (C-SSRS-BL) will be measured at Baseline.

The Columbia-Suicide Severity Rating Scale Since Last Visit Version (C-SSRS-SLV) will be assessed at the post-Baseline visits.

C-SSRS data will only be included in listings and no summary tables created.

### 15.8.2 Impulsive-Compulsive Disorders in Parkinson's Disease—Rating Scale (QUIP-RS)

The QUIP-RS consists of four questions which have to be answered for each disorder (gambling, sex, buying, eating, hobbyism, punning and PD medication use) on a 5-point Likert scale. Scoring range for each scale (i.e. disorder) is 0–16. The total Impulsive Control Disorder (ICD) score and the total QUIP-RS score will be calculated and changes from baseline on these parameters. The individual scores, total scores and changes from baseline in total scores will be presented in listings.

## 15.9 Tolerability

The evaluation of tolerability is based on the following

- The number (%) of subjects who complete the study drug.
  - This analysis includes all premature discontinuations of the study
- The number (%) of subjects who fail to complete the study drug due to AEs
  - This analysis includes the premature discontinuations of the study, in which the primary reason for the premature discontinuation is defined as an AE or death (as defined on the Study Completion case report form page).

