4.2 Withdrawal of Patients from Study Treatment and/or the Study

The duration of the study is defined for each patient as the date signed written informed consent is provided through the last safety follow-up visit at Visit 8. If a patient discontinues treatment, they will be encouraged to remain in the study and continue study visits and procedures for the full course of the study without receiving study treatment. Patients who withdraw from the

study before the Visit 7/ET visit and are not willing to continue study visits and procedures for the full course of the study will be asked, to undergo an ET visit that will include all evaluations that were intended to be performed at the final visit.

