## 6.4 Safety and tolerability endpoints

Following safety and tolerability endpoints will be evaluated. For more details, see section 15 (Analysis of safety and tolerability data).

- Safety
  - Adverse events (AEs) occurring throughout the study.

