## Statistical Analysis Plan

- QTc parameters: absolute QTcF of >450 msec, >480 msec and ≤500 msec, and >500 msec, mean QTcF, changes in QTcF>30 msec and ≤60 msec, and changes in QTcF>60 msec throughout the study.
- Clinical safety laboratory (Only Creatinine Clearance, Serum Creatinine, Potassium and Magnesium), vital signs (including assessment of orthostatic hypotension), physical and neurological examination, concomitant medications throughout the study.
- Columbia-Suicide Severity Rating Scale (C-SSRS)- At baseline and Since last visit throughout the study.
- Change from Baseline (Visit 2) in impulse control disorder as evaluated by the Questionnaire for Impulsive Compulsive Disorders in Parkinson's Disease Rating Scale (QUIP-RS) throughout the study.
- Tolerability
  - The number (%) of subjects who complete the study drug
  - The number (%) of subjects who fail to complete the study drug due to AEs
  - The number (%) of subjects who fail to complete the study drug due to QTcF and QT stopping rules, seizure or convulsions.

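### SAP 15.9 counts two study-drug tolerability endpoints from study discontinuations, so an AE-driven drug stop with continued follow-up would be missed, and it gives no rule for the third endpoint

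*SAP*

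**What the plan says.** SAP 6.4 lists three tolerability endpoints: "The number (%) of subjects who complete the study drug"; "The number (%) of subjects who fail to complete the study drug due to AEs"; and "The number (%) of subjects who fail to complete the study drug due to QTcF and QT stopping rules, seizure or convulsions". All three concern the drug. Protocol 7.3 lists the same three in terms of study treatment. For the detail, SAP 6.4 sends the reader on: "For more details, see section 15 (Analysis of safety and tolerability data").

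SAP 15.9 repeats only the first two and attaches a counting rule to each. For completion of drug: "This analysis includes all premature discontinuations of the study". For failure due to AEs: "This analysis includes the premature discontinuations of the study, in which the primary reason for the premature discontinuation" is an AE or death, "as defined on the Study Completion case report form page". The Study Completion page is named for the second count only; the first names no data source.

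Protocol 4.2 treats stopping drug and leaving the study as different events: "If a patient discontinues treatment, they will be encouraged to remain in the study and continue study visits". Protocol 5.8.1 takes the same line for patients whose blind is broken. Protocol 4.2.1 says its stopping rules may end either treatment or study participation, and its confirmed creatinine-clearance rule ends study treatment.

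**The concern.** The endpoint and its counting rule refer to different events. They give the same answer only if every patient who stops drug also leaves the study, and the protocol is written to avoid that. The patients on whom the two differ are those who stopped drug because of an AE and agreed to stay, which is the group that a tolerability endpoint exists to capture. Leaving them out makes the drug look better tolerated.

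Safety and tolerability by dose remain a stated objective in SAP 3.3. The endpoint that has no rule concerns an event to which the protocol gives special status: Protocol 6.5.1.6 makes discontinuation under the QTcF stopping rules an AE of special interest.

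**Working it through.** The plan states no tolerability rate, so there is no figure to reproduce. The check follows each type of patient through the rules.

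| Patient | Drug basis (SAP 6.4) | Rule in SAP 15.9 | Disposition (SAP 10) and AE overview (SAP 15.3) |
|---|---|---|---|
| Finishes drug and study | Completer | Completer | Completer |
| Stops drug for an AE and leaves the study for it | Non-completer, AE failure | Non-completer, AE failure | Treatment discontinuation, AE |
| Stops drug for an AE and finishes follow-up | Non-completer, AE failure | **Completer, not an AE failure** | Treatment discontinuation, AE |
| Still on drug when the sponsor ends the study | Non-completer, not for an AE | Non-completer if recorded as leaving early, not for an AE | Discontinuation, with its recorded reason |

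The third row is the defect. That patient has no early study discontinuation, so neither rule in 15.9 picks the patient up. SAP 10 counts discontinuation from study or treatment with the primary reason, and SAP 15.3 counts treatment-emergent AEs that led to stopping drug. Both would include the patient, so the report could contradict itself.

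**Could the wording simply be loose?** Possibly, but two things favour the literal reading. The AE rule points to a study-level form, and SAP 10 shows that the authors distinguish study from treatment when they mean to.

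**Third endpoint.** In SAP Section 15, 15.6 summarises QTcF values, categories and changes, and 15.3 counts AEs leading to drug discontinuation in general. Neither counts patients who stopped drug under the QTcF/QT rules or for seizure or convulsions. SAP 17 says that the SAP supersedes the protocol's analyses, but it does not withdraw this endpoint, and SAP 6.4 still lists it.

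**Scale.** Inputs: enrolment below 30 (SAP 9.3; exact number not given), 1:1:1 allocation (SAP 4.2), and percentages taken over all subjects in the group (SAP 9). With N enrolled and equal thirds, one misclassified patient moves a single-dose group's percentage by 100 / (N/3) = 300/N points, and the pooled active group's by 100 / (2N/3) = 150/N points. N is an assumption:

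| N | One dose group | Pooled active |
|---|---|---|
| 29 | 300/29 = 10.3 | 150/29 = 5.2 |
| 24 | 300/24 = 12.5 | 150/24 = 6.25 |
| 18 | 300/18 = 16.7 | 150/18 = 8.3 |
| 15 | 300/15 = 20.0 | 150/15 = 10.0 |

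These denominators are the randomised thirds. The protocol synopsis puts tolerability on the safety set, and SAP 5.2 regroups that set by dose reached. A patient assigned to 150 mg BID who stops during titration can therefore fall in the 100 mg BID group. That group may be larger than a third, with a smaller shift per patient, and the 150 mg BID group smaller, with a larger one.

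**The case against.** The best defence is that the information is not lost. SAP 15.3 gives the number and percentage of subjects whose AEs led to stopping drug, which is close to the second endpoint on the correct basis. SAP 10 gives treatment completion and discontinuation with reasons, which is close to the first. This stands, and it limits the harm to the tolerability table and its conflict with the other two. It does not make the rule in 15.9 right.

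It is also fair to say that no misclassified patient has been shown. Patients are only encouraged to stay, and those unwilling to continue are asked to attend an early termination visit. If nobody stopped drug for an AE and stayed, the AE count is unaffected. The study is now an early-terminated proof of concept, and no decision rule rests on 15.9.

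A reader might infer three stronger points that the documents do not support:

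- **That both counts come from the Study Completion page.** Only the AE count is tied to it. The page is not in the documents, so what else it records is unknown.
- **That patients still on drug at sponsor termination are wrongly classed as non-completers.** They did not finish the planned course, so they are non-completers on a drug basis too. Only the label for the reason is at issue. Neither document says how ongoing patients were recorded.
- **That QTcF goes unanalysed.** SAP 15.6 summarises it in detail. What is missing is the count of drug stops for the named reasons.

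**Conclusion.** The point holds as a defect in a stated rule. SAP 15.9 would count an AE-driven drug stop with completed follow-up as drug completion and omit it from the AE failures, and it leaves the third endpoint in SAP 6.4 without a derivation or row. The tolerability table could understate AE-related drug stops and disagree with the disposition and AE overview tables. Whether it would in fact do so is unknown, because the documents do not give the number of such patients.

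For scale, one such patient would move a dose group's rate by roughly 10 points or more, assuming fewer than 30 patients in near-equal thirds. The figure is illustrative because of the regrouping in SAP 5.2. The matter should be corrected, but it does not threaten the study's main conclusions, since related counts on the drug basis appear elsewhere in the SAP.

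**What to change.** Revise SAP 15.9 before database lock and unblinding:

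1. Derive drug completion, and failure to complete due to AEs, from the treatment-discontinuation record and its primary reason, consistent with SAP 10 and SAP 15.3.
2. Add a row for the third endpoint in SAP 6.4, and name the records that identify drug stopped for QTcF/QT stopping rules, seizure or convulsions.
3. Show non-completion due to sponsor or COVID-19 termination as its own reason, so that it is not read as intolerance.

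The first and third items need only wording and table programming, because SAP 10 already requires treatment discontinuation and its primary reason. The second needs a short derivation; the case report form is not in the documents, so the source fields have to be confirmed. No clinical rule changes and no new patient data are proposed.

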4.2.1 Reasons for Withdrawal/Discontinuation

Patients are free to withdraw from the study at any time and for any reason without prejudice. The investigator also has the right to withdraw a patient from the study if an intercurrent illness or AE occurred, if the patient did not cooperate, or for any reason concerning the health or well-being of the patient. The reasons for patients not completing the study will be recorded.

Among other reasons, a patient may be discontinued from the study treatment or the study if they meet any of the following stopping rules:

QTcF stopping rules

- QTcF >500 msec (based on the mean value from the triplicate ECG measurements)
- QTcF >480 msec with concurrent increase in QTcF >60 msec (Δ QTcF, based on the mean value from the triplicate ECG measurements) from Baseline (Visit 2)
- Patients with QTcF >480 msec or with an increase of QTcF >60 msec from Baseline (Visit 2) will return to the clinic within 48 to 72 hours for repeat evaluation of electrolyte levels and repeat triplicate ECGs to demonstrate reversibility of the effect on QTcF. Decision on discontinuation will be determined by EAC

Creatinine clearance stopping rule

Patients with an adjusted CrCL <50 mL/min/1.73 m² calculated by CrCL * BSA/1.73, where CrCL is calculated using the Cockcroft-Gault equation $[(140 - \text{age}) \times \text{mass (kg)} \times [0.85 \text{ if female}] / 72 \times \text{serum creatinine (mg/dL)}]$ at any time point after Baseline (Visit 2) will be requested to return to the clinic for an unscheduled visit 1 week later to repeat the CrCL test one more time for confirmation. If the repeated CrCL value is confirmed to be <50 mL/min/1.73 m², the patient will be discontinued from the study treatment.

The investigator will also withdraw a patient if Prilenia Therapeutics or regulatory authorities terminate the study. If a patient is discontinued because of an AE, the event will be followed until it has resolved.

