## Statistical Analysis Plan

In the AE summaries, data will be presented in four columns (pridopidine 150 mg BID, pridopidine 100 mg BID, pridopidine total, placebo) using the Safety Population.

The following summaries will be provided. If not stated otherwise, the tables will be sorted in alphabetic order by SOC, and within each SOC, in descending order according to the % of subjects reporting each PT in the pridopidine total group.

- An overall summary of the number and percentage of subjects reporting TEAEs and the number of TEAE events, treatment-related TEAEs, severe TEAEs, TEAEs leading to death (if there are any subjects who died), SAEs other than death, TEAEs leading to study drug discontinuation and TEAEs leading to temporary withdrawal
- The incidence (number and % of subjects) and frequency (event count) of TEAEs broken down by System Organ Class (SOC) and PT.

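### SAP 15.9 derives its study-drug tolerability endpoints from study discontinuation, so a patient who stops drug for an AE but stays in the study is misclassified

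*SAP*

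**What the plan says.** SAP 6.4 lists three tolerability endpoints, all defined on study drug, and Protocol 7.3 lists the same three on study treatment. The second is "The number (%) of subjects who fail to complete the study drug due to AEs". The third counts subjects "who fail to complete the study drug due to QTcF and QT stopping rules, seizure or convulsions".

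SAP 15.9 keeps the study-drug labels for the first two but gives rules based on the study. For completing study drug the rule is "This analysis includes all premature discontinuations of the study". For AE-related failure, the count "includes the premature discontinuations of the study, in which the primary reason for the premature discontinuation is defined as an AE or death", with the reason taken "as defined on the Study Completion case report form page". The third endpoint has no rule in 15.9.

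The protocol keeps the two events apart. Section 4.2 states: "If a patient discontinues treatment, they will be encouraged to remain in the study and continue study visits and procedures", without receiving drug. In 4.2.1, after a confirmed low creatinine clearance, "the patient will be discontinued from the study treatment"; leaving the study is not mentioned.

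The SAP makes the same distinction elsewhere. Its Section 10 disposition table covers discontinuation from the study or from treatment, each with a primary reason. The AE overview in 15.3 has a row for "TEAEs leading to study drug discontinuation".

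**The concern.** A drug-tolerability endpoint should count people who stopped the drug. A rule that counts people who left the study gives the same answer only if everyone who stops drug also leaves at that point for the same recorded reason. This protocol asks patients not to do that.

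At stake is whether the clinical study report carries one consistent account of AE-related drug stopping. The 15.9 figure could differ from the disposition table and the AE overview, and the SAP does not say which governs. The completion endpoint has the same fault as the AE endpoint. SAP Section 2 says that the SAP overrides the protocol where they differ, but that does not settle the matter, because 15.9 is at odds with the SAP's own 6.4. SAP 17 does not identify a change to this endpoint.

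**Working it through.** The plan states no figure for this endpoint, so there is none to reproduce. The check applies the 15.9 rules literally to possible patient records and then sizes one misclassified patient.

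**Step 1. Literal application.** Assumption: the Study Completion page records whether and why the subject left the study, as its name suggests. The form itself is not in the documents. Days follow the Amendment 1 schedule.

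| Record | Completed drug: actual | Completed drug: 15.9 | AE stop: actual | AE stop: 15.9 |
|---|---|---|---|---|
| A. Stops drug for an AE in Week 6, stays through Visit 8 | No | Yes | 1 | 0 |
| B. Stops drug for an AE, stays, participation ended by sponsor termination | No | No | 1 | 0 |
| C. Stops drug for an AE and leaves the study at once for that AE | No | No | 1 | 1 |
| D. Takes all drug including down-titration, leaves for an AE before Visit 8 | Yes | No | 0 | 1 |

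Only record C is classified correctly on both endpoints. A is wrong on both, and B is wrong on the AE count. D errs the other way. Visit 7 is Day 112 and down-titration lasts 4 days, so drug ends on Day 112 + 4 = Day 116. Record D can therefore arise only from about Day 117 to Visit 8 on Day 126. If down-titration is not part of completing study drug, the window for D opens at Visit 7. The SAP does not say which applies.

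**Step 2. Size of one patient.** SAP 9.3 says that the study ended before 30 subjects were enrolled, and allocation was 1:1:1.

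- Average arm: fewer than 30 / 3 = fewer than 10 subjects, so one patient is at least 1/10 = 10 percentage points of an average arm.
- Two active arms pooled: fewer than 20 subjects if arms are equal, so one patient is at least 1/20 = 5 percentage points.

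The actual group sizes are not given. SAP 5.2 groups safety subjects by regimen reached, so the groups need not be equal.

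**Step 3. Dependence on the share who stay.** Let *s* be the share of AE drug-stoppers who remain in the study. Ignoring record D, the expected 15.9 count is the true count × (1 − *s*). As an illustration, assume 10 subjects in an arm and 2 AE drug stops, a true rate of 2/10 = 20%:

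| *s* | 0 | 0.25 | 0.50 | 0.75 | 1 |
|---|---|---|---|---|---|
| Expected reported rate | 20% | 15% | 10% | 5% | 0% |

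The documents give neither the number of AE drug stops nor *s*. The table shows how the rule behaves and does not estimate this trial's error.

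**Step 4. Comparison with the other tables.** SAP 10 would record A and B as treatment discontinuations with their primary reason. SAP 15.3 would count their TEAEs as leading to drug discontinuation. SAP 15.9 would not count either patient as an AE failure, so the report would contain counts that disagree with no rule for resolving them.

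**The case against.** **The form is unseen, and another reading exists.** Protocol 7.7 and 7.9.1 describe retrieved drop-out data as collected after an end-of-study visit, once the patient is off treatment. On that usage, a patient who stops drug could have an end-of-study record giving the AE as reason and still be followed. Record A would then be counted correctly. This lowers certainty but does not remove the conflict. SAP 15.9 names discontinuation of the study, and Protocol 4.2 asks for the early termination visit only from patients who withdraw and will not continue visits.

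**The information is not lost.** SAP 10 and 15.3 already report drug stopping and its reasons, so a reader can compare AE-related stopping across arms whatever 15.9 gives. This stands. It limits the harm to a wrong or inconsistent endpoint figure.

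**Stronger readings a reader might infer.** One is that this is the trial's main tolerability measure. The documents list three unranked items and attach no test or decision rule to them. Another is that the error makes the drug look better tolerated because AE stops fall mainly on active arms. The documents give no AE-stop rates by arm, and record D shows that the error can also run the other way. A third is that some patients were probably missed. That needs an assumed stop rate and staying share. The protocol only encourages staying, so the share may be zero.

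**Not every treatment-only stop is an AE stop.** The creatinine clearance rule is a laboratory threshold; Protocol 6.8 makes a decrease an AE only if the investigator judges it clinically significant. Unblinding (Protocol 5.8.1) also stops drug but is not an AE reason. These rules show that stopping drug and leaving the study are separate events, and nothing more.

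**Conclusion.** The point holds as a fault in a stated derivation. SAP 15.9 labels two endpoints by study drug and derives both from leaving the study, in a trial that asks patients who stop drug to stay. Followed as written, it misclassifies a patient who stops drug for an AE and remains.

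The conclusion rests on the literal text of 15.9 and on the Study Completion page recording study rather than drug discontinuation. The number affected is unknown and may be zero. If arms are about equal, each such patient shifts an arm's figure by roughly 10 percentage points. The primary efficacy analysis is not touched.

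Separately, the third endpoint in SAP 6.4 has no derivation in 15.9. That gap does not depend on how many patients stayed or on how the form is read.

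**What to change.** In SAP 15.9:

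1. Derive both endpoints from one source: the treatment-discontinuation record used for SAP 10. A subject fails to complete study drug if that record shows a premature stop. The failure is AE-related if its primary reason is AE or death. Apply this whether or not the subject stayed in the study.
2. State whether the 4-day down-titration counts towards completing study drug.
3. Reconcile the AE count with the 15.3 row by patient and explain any difference. The two need not match: one uses the primary reason for stopping, the other is a count of TEAEs that led to stopping. Merging the two sources into one count would not make it equal to the 15.3 row.
4. Tabulate the third endpoint from SAP 6.4 (QTcF/QT stopping rules, seizure or convulsions) from the same record.

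The cost is a change of wording and a small re-programming task on data already planned for tabulation. SAP Section 2 says that the SAP is being finalised before lock and unblinding, so the change can be made blind. The reported AE-discontinuation figure may become less favourable. No clinical rule changes.
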